Study Title: Treatments of Acquired Apraxia of Speech

NCT #: NCT01483807

Document: Study Protocol

Date of last protocol approval by IRB: November 22, 2015

Protocol:

Participants

Inclusion Criteria:

- At least 6 months post onset of focal brain injury
- Chronic acquired apraxia of speech and aphasia
- Native English speaker
- Age: 21 85 years
- Pure tone hearing adequate to pass screening at 35 dB at 500, 1000, and 2000 Hz
 least one ear, or if aided, or verification from an audiological examination that
 hearing was adequate for conversational level speech.
- Negative histories for alcohol and/or substance abuse and neurological conditions other than stroke; self-reports verified by medical record review
- Performance within normal limits on the *Test of Nonverbal Intelligence-4* (Brown, Sherbenou, & Johnsen, 2010).

AOS diagnostic criteria (McNeil, Robin, & Schmidt, 1997; 2009)

- Slow rate of speech
- Sound errors which included a predominance of distortions
- Syllable segregation
- Relatively consistent trial-to-trial articulation errors
- Prosodic abnormalities.

A battery of tasks was administered to elicit speech samples from which to judge presence/absence of AOS characteristics: 1) *Apraxia Battery for Adults-2* (Dabul, 2000), 2) word and sentence repetition tasks (Wambaugh, Kalinyak-Fliszar et al., 1998; Wambaugh, West,

& Doyle, 1998; and Mauszycki & Wambaugh, 2008, and 3) discourse production (Nicholas & Brookshire, 1993). AOS symptoms were evident in at least some, but not necessarily all, of the preceding speech elicitation tasks. The diagnosis of AOS was initially made by each participant's primary clinician (one of the authors) and then was verified by the first author.

Language assessments:

- Western Aphasia Battery-Revised (WAB-R; Kertesz, 2007)
- *Porch Index of Communicative Ability (PICA*; Porch, 2001)
- Nicholas & Brookshire Discourse Elicitation Battery (Nicholas & Brookshire, 1993)

Demographic data collected:

- Age
- Months post-onset
- Etiology
- Area of brain damage
- Years of Education
- Premorbid handedness
- Race/ethnicity
- Hemiparesis
- Marital status

Experimental Design

A combined group and SCED was used. The group design component was a two-phase, cross-over design and the SCED component was a multiple baseline designs (MBD) across behaviors and participants. This report is focused on the results of the group design. However,

probe data from the SCEDs will be provided in the supplemental materials for the 10 participants whose data have not been reported previously.

Accuracy of articulation of two sets of experimental words (see "Experimental Stimuli") was measured repeatedly prior to treatment (see "Probes" for additional detail). For each participant, treatment (SPT-Random [SPT-R] or SPT-Blocked [SPT-B]) was then applied to one set of experimental words while probing continued with both experimental sets. A two week, notreatment interval followed the first treatment phase and a short-term maintenance probe was completed at the end of the interval. Repeated probing of the set of items to be treated in the second treatment phase during the no treatment interval (as part of the SCED) ensured that performance was stable prior to the application of treatment with that set. Then, the alternate treatment was applied to the remaining set of items. Follow-up probes were conducted at 2, 6, and 10 weeks following the second treatment phase. Please see Wambaugh et al. (2014, 2016) for description of the SCED component.

Treatment Order and Experimental Set Assignment. Quasi-randomized assignment was combined with participant matching to assign participants to one of two treatment orderings (i.e., SPT-R → SPT-B or SPT-B → SPT-R). We aimed to have a balance of aphasia type, aphasia severity and AOS severity reflected in the treatment orders. The first participant enrolled was randomly assigned to a treatment condition. Each subsequently enrolled participant was "matched" to a previously enrolled participant and assigned to the opposite group if he/she had the same aphasia type, had an AQ within 10 points of the match, and had the same AOS severity rating. When a match did not exist, then the participant was randomly assigned to a treatment order. Treatment order assignment is shown in Table 2. Participant matching for treatment order is shown in Supplemental Appendix B: aphasia severity was within 10 AQ points for 8/10

matches, aphasia type was the same for 9/10 matches, and AOS severity was the same for 8/10 matches. Please note that the purpose of the investigation was not to compare performance across groups as all participants received both treatments. The matching and random assignment was conducted to minimize possible confounds associated with treatment order.

In the development of the stimuli, it was not expected that participants would be able to produce all other sounds in the experimental word, other than the target sound(s), correctly. Errors could, and did, occur on non target sounds. All target sounds for a given participant were considered in stimuli selection. For words representing a given target, we tried to avoid inclusion of the other targets. For example, if the targets were /bl, sw, m, n/, in the selection of /bl/ words, we avoided words that contained /sw/, /m/, or /n/. It was not always possible to exclude other target sounds, particularly with multisyllabic words. Within participant, lists were balanced as closely as possible for syllable length and position of the target sound within the word (e.g., initial, medial, or final). The experimental sets were also balanced as much as individual variation allowed for singletons versus clusters, manner, and place of production. For example, if one experimental set had a subset representing a particular cluster, then the other experimental set also had a subset with a cluster. Possible generalization effects were also considered in the selection of stimuli with choices made to avoid generalization across lists. For example, if /pl/ was selected for one list, then none of the other lists would be comprised of /l/ blends or /p/ or /b/ words. Words were not balanced for frequency or familiarity due to other constraints. It is recognized that such balancing would have been preferable and was initially attempted, but could not be achieved. The nature of the experimental tasks (i.e., repetition) and the experimental design assuaged our concerns over familiarity and frequency somewhat; these potential confounds would have been present across all study phases (e.g. increased familiarity through repeated exposure should have been revealed in the baseline phase). A variety of databases and dictionaries were used to develop stimuli lists.

Probes. Production of the experimental words was elicited in probes. During probes the examiner presented each word verbally, one at a time in random order, and asked the participant

to repeat the word as accurately as possible. No feedback concerning accuracy of production was provided; only general encouragers (e.g., you're trying hard) were used. The treatment items were included in probes to measure the *acquisition effects* of treatment and the untreated exemplars of trained items were used to measure the *response generalization* effects of treatment (see Dependent Variable). Note that the term "acquisition" is used to represent probe performance with treated items and not performance during treatment and as such is analogous to the term "retention" as used in the motor learning literature. All probe sessions were audio recorded.

Blinded examiner probes. An investigator who was blinded to the assignment of experimental words to treatment condition conducted probes identical to the probes described above. One blinded probe was completed during the baseline phase and at the end of each treatment phase.

Dependent Variable

The dependent variable was accuracy of articulation of a target sound or sounds produced in words, with a single score of correct or incorrect being used for each experimental item.

Scoring was completed using on-line, modified narrow transcriptions supplemented and verified with audio recordings (e.g., Haley, Bays, & Ohde, 2001). The target sound(s) for each experimental word was/were identified and determined to be accurately or inaccurately produced on the basis of the transcription. Then, the word containing the target sound(s) was given a score of "correct/incorrect". For each subset of items for each participant, the percentage of words in which the target sounds(s) was produced correctly was tallied from the verified, online productions; the subsets were further separated into trained and untrained subsets. These percentages served as the dependent variables for all analyses.

Target sounds were required to be produced without distortion in the correct syllable of the word. Multisyllabic words were required to have the correct number of syllables so that location accuracy could be judged. For words embedded in a phrase, the phrase word had to be attempted in order for the target sound (in the other word member of the phrase) to be scored as accurate. However, accurate production of the non-targeted phrase word was not required.

The *first complete* production was scored. If the entire target item was produced and there was an error on the target sound(s) and then the participant self-corrected the error, that item was scored as incorrect. However, if there was a false-start (the entire target item was not produced initially) followed by a correct production, then the complete production was scored as correct

For the majority of the participants, accuracy of production of the one target sound/cluster per word was scored. However, for a subset of four participants with multisyllabic words targets (two participants from each of the treatment orderings), accuracy of production of all consonants in the word was required to achieve an overall score of correct production (Wambaugh et al., 2016). These four participants had mild to mild-moderate AOS and sometimes had greater than 50% accuracy of production of specific target sounds in baseline. In order to have sufficient numbers of errors to demonstrate change with treatment, all consonants were scored/targeted.

The experimenter who conducted the probe completed the online scoring of that probe.

During the treatment phases, these experimenters also provided treatment. These same experimenters also conducted the baseline and follow-up phase probes when there was no treatment. That is, the same experimenters were used to conduct all probes throughout all phases of the study for a given participant. Ideally, experimenters who were blinded to the assignment

of items to treatment would conduct all probes, but this was logistically and economically infeasible. Consequently, a limited number of blinded probes were conducted (as described previously). With the blinded probes, the examiner was not involved in treatment.

Treatment

SPT utilizes the therapeutic techniques of modeling/repetition, contrastive practice, orthographic cueing, integral stimulation, and articulatory cuing. These techniques are applied using a response-contingent hierarchy as follows:

- 1. The speech/language pathologist (SLP) produces a verbal model of the word or phrase and requests a repetition. If monosyllabic words are the treatment targets, substeps are used for the purposes of contrastive practice upon an incorrect production (e.g., Wambaugh & Mauszycki, 2010; Wambaugh & Nessler, 2004). If multisyllabic words are the target, then contrastive practice is not used and the next step is attempted.
- The SLP uses printed letters/word to indicate the sound in error, directs the participant to attend to the target sound, provides another verbal model, and requests a repetition.
- 3. The SLP uses integral stimulation "watch me, listen to me, say it with me" and attempts simultaneous production until a correct production is achieved, with a maximum of three attempts. In cases where a phrase is used, the entire phrase is attempted.
- 4. The SLP provides articulatory cuing appropriate for the sound production error and then repeats the procedures used in the previous step. Only the target word is practiced (not the entire phrase).

5. The SLP presents the next item.

Verbal feedback concerning the correctness of production of the sound target is provided immediately after each response. Since the hierarchy is response-contingent, ensuing steps of the hierarchy are completed *only* after an erroneous production. Following a correct response and provision of feedback, the next item is presented. The steps of the hierarchy are not reversed following a correct response. In previous SPT investigations (Wambaugh & Mauszycki, 2010; Wambaugh & Nessler, 2004), multiple productions of the target word were elicited upon a correct response at any step of the hierarchy. In the current study, the multiple repetitions following a correct response were not elicited because these could be considered a form of blocked practice.

As indicated in Step 1, when SPT is applied to monosyllabic words, the first step includes a sub step in which a minimal contrast word that reflects the sound error is practiced (see Wambaugh & Mauszycki, 2010 or Wambaugh & Nessler, 2004). Minimal contrast is not used when the targets are multisyllabic words because real word minimal pairs are rarely possible. Participants with monosyllabic treatment stimuli completed this sub step of Step 1.

The SPT hierarchy was applied to each treatment item repeatedly in a treatment session. For SPT-R, SPT was applied to all 20 treatment items (10 words for each target) by alternating between the subsets randomly. For SPT-B, SPT was applied to each of the 10 words in a subset before treatment was applied with the other subset. Within subset, the words were presented in random order for SPT-blocked. For four of the participants (two from each of the treatment ordering groups), a modification was made to the blocking procedure; blocking was applied to each word so that each word was practiced for five minutes (please see Wambaugh et al., 2016 for rationale and description of procedure).

The treatment sessions were 50 to 60 minutes long excluding probes. One treatment trial consisted of application of the SPT hierarchy to each of the treatment items. As many treatment trials as possible were completed in the 50-60 minute time period. The number of treatment trials per session varied within and across participants and corresponded to the number of errors that occurred because more errors required use of more steps of the hierarchy. Therefore, participants completed more trials per session toward the end of a treatment phase in comparison to the initial treatment sessions with a phase. Although number of treatment trials varied, the length of each treatment session was carefully controlled and was consistent within and across participants.

Number of treatment sessions was equivalent across treatment phases for each participant. Eighteen of the participants received 20 treatment sessions per phase and two participants received 10 treatment sessions per phase (P5 & P15; Wambaugh et al., 2016). The shorter length of treatment was due to a rapid treatment response. For clinical purposes, it would likely be desirable to administer the necessary number of treatment sessions to achieve a desired level of performance (rather than have a pre specified number of sessions). However, in the current investigation, lack of equivalency of number of sessions per condition for each participant could have confounded our findings.

ASHA certified research SLPs conducted treatment sessions three times per week. For one participant (P2), a master's student provided treatment for a portion of the sessions; this student was supervised 100% of the time by the third author who also provided treatment.

Accommodations to treatment schedule were made as needed (e.g., illness, vacations, holidays). Each participant selected his/her treatment location which remained constant throughout the study (i.e., participant's residence, research laboratory, or university clinic).

Reliability

Dependent Variable. Twenty percent of all probes (including all SCED probes) were quasirandomly selected for rescoring by a research SLP who had not provided treatment; random
selection occurred for all phases of the study. The audio recordings of probe sessions were used
for rescoring. The reliability SLP was blinded to the assignment of lists to treatment phase and to
assignment of items as treated or untreated. Point to point agreement was calculated for scoring
of each item and percent agreement was calculated for each probe. Agreement for scoring each
word/target as correct/incorrect ranged from 85% to 96%, with the average being 91%.

Independent Variable. A research SLP who had not participated in a given participant's
treatment scored audio recorded treatment sessions for accuracy of implementation of treatment.

Ten percent of all treatment sessions were randomly selected and were scored for administration
of specific treatment components: 1) correct application of steps of the treatment hierarchy –

99.6 %; 2) presentation of target words (all words presented in each trial) – 99.8%; 3) session
length of 50-60 minutes within +/- 1 minute – 100%; and 4) accurate application of blocking and
randomization – 100%.

## **Statistical Analyses**

## **Effect Sizes**

Six separate sets of effect size values were calculated for each participant as an indication of magnitude of change for *treated items*: 1) pre-treatment/baseline vs. end of SPT-R treatment phase – Random Phase Items – both subsets; 2) pre-treatment vs. 2-week follow-up – Random Phase Items – both subsets; 3) pre-treatment vs. 10-week follow-up – Random Phase Items – both subsets, 4) pre-treatment vs. end of SPT-B treatment phase – Blocked Phase Items – both subsets; and 5) pre-treatment vs. 2-week follow-up – Blocked Phase Items – both subsets; and 6) pre-treatment vs. 10-week follow-up – Blocked Phase Items – both subsets. This resulted in twelve Δ-values for treated items per individual. Six additional sets of effect size values were also calculated for untreated (generalization) items with comparisons being analogous to those of treatment items.

For the pre-treatment versus end of treatment comparisons, the five baseline probes immediately preceding application of treatment were used along with the final two probes completed during the treatment phase. For the pre-treatment versus two-week follow-up comparisons, the five baseline probes immediately preceding treatment were used with the 2-week follow-up probe that followed completion of that phase of treatment. For the 10-week comparisons, the five baseline probes immediately preceding the treatment phase were also used with the probe that occurred 10 weeks following the treatment phase. Because the experimental design was a cross-over design with only a two-week no-treatment interval, the 10-week follow up probes for the first treated sets fell at approximately two weeks after the conclusion of all treatment (i.e., there was not a 10-week no treatment interval and 10 weeks after the first treatment phase occurred about 2 weeks after the second treatment phase). For the second treated sets, the 10-week follow up

probes were those conducted at 10 weeks following all treatment. For the two participants with shortened treatment phases, the 10 week follow-up point for the first phase of treatment fell at approximately 6 weeks post all treatment.

The  $\Delta$ -values were derived using the following equation:  $ES = (M_{A2} - M_{A1}) / SD_{A1}$ . In this equation, "A1" indicates the baseline values and "A2" indicates the comparison values (i.e., end of treatment, 2 week follow up, or 10 week follow up).

For each participant, the two Δ-values for each subset within each experimental set were averaged to obtain one effect size per participant for each comparison condition. Tables 1 and 2 display the average effect size, SD of effect sizes, minimum and maximum effect sizes for the group of 20 participants for the treated items and generalization items, respectively. Relative to SPT benchmark effect sizes recently described by Bailey, Eatchel, and Wambaugh (2015) medium effect sizes were found for baseline to treatment phase comparisons for treated items for the group for both SPT-R and SPT-B (SPT-R = 9.203 and SPT-B = 7.389). For the two week follow-up phase comparison, a medium effect size was found for SPT-R (8.643) and a small effect size was found for SPT-B (6.861). For the 10 week follow-up comparison, small effect sizes were found for SPT-R (6.84) and SPT-B (6.144). For untreated items, small effect sizes were found for both SPT-R and SPT-B in all instances for the group (Table 4). As reflected by the minimum and maximum values in Tables 1 and 2, there were wide ranges of effect sizes found across the individuals.

Table 1

Effect Size (Δ-values) Descriptive Statistics for **Treated Items** by Treatment Condition for the Group of 20 Participants

Condition	Comparison	Mean	SD	Minimum	Maximum		
		$\Delta$ -values					
Random	BL vs Tx	9.203	4.344	2.766	18.244		
	BL vs 2 wk FU	8.643	5.204	1.469	21.019		
	BL vs 10 wk FU	6.84	3.99	1.66	18.78		
Blocked	BL vs Tx	7.389	3.754	1.341	13.868		
	BL vs 2 wk FU	6.861	3.533	2.109	15.199		
	BL vs.10 wk FU	6.144	3.299	.830	14.378		

 $\overline{BL}$  = baseline; Tx = treatment; wk = week

Bailey et al. (2015) benchmarks: small = 5.23, medium = 6.98, large = 9.65 for baseline to treatment phase comparisons and small = 5.90, medium, = 7.12, large = 10.19 for baseline to follow-up phase comparisons

Table 2

Effect Size (Δ-values) Descriptive Statistics for Generalization Items by Treatment Condition for the Group of 20 Participants

Condition	Comparison	Mean	SD	Minimum	Maximum
		Δ-values			
Random	BL vs Tx	3.68	3.162	274	10.757
	BL vs 2 wk FU	3.452	2.711	483	8.367
	BL vs. 10 wk FU	2.556	2.615	293	9.839
Blocked	BL vs Tx	3.083	3.011	.0424	10.168
	BL vs 2 wk FU	3.074	2.865	771	8.721
	BL vs. 10 wk FU	2.107	2.466	771	7.826

 $\overline{BL} = baseline; Tx = treatment; wk = week$ 

Bailey et al. (2015) benchmarks: small = 2.25, medium = 3.75, large = 6.66 for baseline to treatment phase comparisons and small = 2.59, medium, = 4.23, large = 6.47 for baseline to follow-up phase comparisons

Paired t-tests with were utilized to compare the effect sizes obtained for SPT-R versus SPT-B. Normality tests were passed and one-tailed p values were obtained. There was not a significant difference in the sample means for *treated item* effect sizes associated with the end of treatment (p = .08), 2-week follow-up phases (p=.105), or 10-week follow up phases (p=.254) for SPT-R treated items versus the SPT-B treated items.

For the *untreated* (generalization items), there were also no significant differences in the sample means for the three measurement conditions: end of treatment – p = .186; 2-week follow-up – p = .236; and 10-week follow-up – p = .212.

For all paired t-tests describe above, power was below the desired power of .80 and negative findings should be interpreted cautiously.

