## **Percent Change Over Highest Baseline Performance**

In order to provide clinically interpretable indicators of degree of change associated with treatment, percent change scores were calculated. Separate calculations were made for each experimental set of items separated by subgrouping (SPT-R treated, SPT-R untreated, SPT-B treated, SPT-B untreated). For each participant, the highest percent accuracy score achieved in baseline was subtracted from the a) last treatment probe, b) the 2 week follow-up probe, and c) the 10 week follow-up probe. Tables 3 and 4 depict the average change scores for the group for the treated and untreated items. A negative value in Tables 3 and 4 indicates that the follow-up value was less than the highest baseline value. Note that the median scores for the group were all positive as were the 25th percentile values.

Table 3

Percent Change Over Highest Baseline: Descriptive Statistics for **Treated Items** by Treatment Condition for the Group of 20 Participants

Condition	Comparison	Mean	SD	Minimum	Maximum	Median	25 th	75 th
							%tile	%tile
Random	BL vs Tx	65.5%	20.7%	20%	100%	60%	50%	80%
	BL vs 2 wk FU	58.5%	29%	0%	100%	60%	40%	87.5%
	BL vs 10 wk FU	46.25%	32.1%	-20%	100%	50%	20%	85%
Blocked	BL vs Tx	51%	29.8%	-10%	100%	50%	30%	80%
	BL vs 2 wk FU	45.8%	29.5%	-20%	100%	40%	20%	70%
	BL vs 10 wk FU	38.0%	26.3%	-20%	80%	40%	12.5%	60%

BL = baseline; Tx = treatment; wk = week

Table 4

Percent Change Over Highest Baseline: Descriptive Statistics for Generalization (Untreated) Items by Treatment Condition for the Group of 20 Participants

Condition	Comparison	Mean	SD	Minimum	Maximum	Median	25 th	75 th
							%tile	%tile
Random	BL vs Tx	24.3%	41.7%	-67%	100%	20%	0%	60%
	BL vs 2 wk FU	23.8%	40.5%	-67%	100%	37%	0%	55%
	BL vs 10 wk FU	14.15	35.2%	-60%	100%	0%	0%	30.5%
Blocked	BL vs Tx	24.5%	41.4%	-33%	100%	20%	0%	55%
	BL vs 2 wk FU	22.7%	33.8%	-40%	100%	20%	0%	40%
	BL vs 10 wk FU	12.5%	32.7%	-60%	80%	0%	0%	34%

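### Two SAP sentences describe untreated (generalization) items more favourably than the SAP's own Tables 2 and 4, mainly at 10 weeks

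*SAP*

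**What the plan says.** Two sentences in the SAP summarise results for untreated items.

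- **Effect Sizes.** After labelling the treated-item means against published benchmarks, the SAP says: "For untreated items, small effect sizes were found for both SPT-R and SPT-B in all instances for the group (Table 4"). The untreated effect sizes are in Table 2, titled "Descriptive Statistics for Generalization Items by Treatment Condition for the Group of 20 Participants". The note below that table gives the follow-up benchmarks as "small = 2.59, medium, = 4.23, large = 6.47 for baseline to follow-up phase comparisons"; its small value for the end of treatment is lower, at 2.25.
- **Percent Change Over Highest Baseline Performance.** Table 3 (treated items) and Table 4 (untreated items) are introduced together. The SAP explains: "A negative value in Tables 3 and 4 indicates that the follow-up value was less than the highest baseline value". The next sentence begins "Note that the median scores for the group were all positive as were the 25" and goes on to name the 25th percentiles. Nothing in it restricts the statement to treated items.

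The Protocol, under Probes, explains why these items were probed: "untreated exemplars of trained items were used to measure the *response generalization* effects of treatment".

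**The concern.** Neither sentence agrees with the table it summarises. At 10 weeks both untreated mean effect sizes are below the printed small benchmark, although the text calls every one of them small. Table 4 contains zeros where the text says all values are positive. The pointer to Table 4 sends the reader to percent-change data, where the effect-size label cannot be checked.

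Response generalization is one of the two effects the probes were designed to measure; the other is acquisition. Both discrepancies favour the untreated items, and they coincide at 10 weeks, where the tabulated results are weakest. A reader who relies on the text alone would believe that a benchmark-level effect persisted at 10 weeks and that the typical participant was still above the best baseline score. A 0% median means that at least half of the values in that row are at or below the highest baseline score.

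**Working it through.** **1. Labelling rule, checked on treated items.** Inputs are the Table 1 means and the benchmarks in the note to Table 1: 5.23 / 6.98 / 9.65 for treatment phase and 5.90 / 7.12 / 10.19 for follow-up (small / medium / large). Rule: a mean takes the highest category whose benchmark it reaches.

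| Treated mean | Benchmarks | Result | SAP label |
|---|---|---|---|
| SPT-R, end of treatment, 9.203 | 6.98 to 9.65 | medium | medium |
| SPT-B, end of treatment, 7.389 | 6.98 to 9.65 | medium | medium |
| SPT-R, 2 weeks, 8.643 | 7.12 to 10.19 | medium | medium |
| SPT-B, 2 weeks, 6.861 | 5.90 to 7.12 | small | small |
| SPT-R, 10 weeks, 6.84 | 5.90 to 7.12 | small | small |
| SPT-B, 10 weeks, 6.144 | 5.90 to 7.12 | small | small |

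The rule reproduces 6 of 6 labels. A nearest-benchmark rule reproduces 3 of 6: it would call 9.203 large, and 6.84 and 6.861 medium.

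**2. The same rule on untreated items.** Inputs are the Table 2 means and the benchmarks in its note.

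| Untreated mean | Small benchmark | Difference | Result |
|---|---|---|---|
| SPT-R, end of treatment, 3.68 | 2.25 | +1.430 | small (below 3.75) |
| SPT-B, end of treatment, 3.083 | 2.25 | +0.833 | small |
| SPT-R, 2 weeks, 3.452 | 2.59 | +0.862 | small (below 4.23) |
| SPT-B, 2 weeks, 3.074 | 2.59 | +0.484 | small |
| SPT-R, 10 weeks, 2.556 | 2.59 | -0.034 | below small |
| SPT-B, 10 weeks, 2.107 | 2.59 | -0.483 | below small |

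Four of six are small and two are below small. The shortfalls are 0.034 / 2.59 = 1.3% for SPT-R and 0.483 / 2.59 = 18.6% for SPT-B.

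Two alternatives do not restore six small labels. Using the treatment-phase benchmark of 2.25 at follow-up rescues SPT-R but not SPT-B (2.107). The nearest-benchmark rule would call 3.68, 3.452 and 3.083 medium.

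**3. Precision of the two 10-week means, for context.** With n = 20 and t(19) = 2.093, SE = SD / √20.

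- SPT-R: SE = 2.615 / 4.472 = 0.585; 2.556 ± 1.224 gives 1.33 to 3.78.
- SPT-B: SE = 2.466 / 4.472 = 0.551; 2.107 ± 1.154 gives 0.95 to 3.26.

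Both approximate 95% intervals include 2.59 and exclude zero. The SAP labels point estimates, so this does not decide the label. It does show that the shortfalls support no stronger conclusion.

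**4. Medians and 25th percentiles of percent change.**

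| | SPT-R: end, 2 wk, 10 wk | SPT-B: end, 2 wk, 10 wk | Above 0 |
|---|---|---|---|
| Table 3 median (%) | 60, 60, 50 | 50, 40, 40 | 6 of 6 |
| Table 3 25th percentile (%) | 50, 40, 20 | 30, 20, 12.5 | 6 of 6 |
| Table 4 median (%) | 20, 37, 0 | 20, 20, 0 | 4 of 6 |
| Table 4 25th percentile (%) | 0, 0, 0 | 0, 0, 0 | 0 of 6 |

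Of the 24 values, 16 are positive and 8 are zero. All 8 zeros are in Table 4 (2 medians and 6 lower quartiles). That table prints minus signs elsewhere, so the zeros do not look like a fault in reading the PDF.

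**The case against.** The strongest objection concerns the meaning of the small benchmark. Every treated mean exceeds its small value (the closest is 6.144 against 5.90), so the treated labels never test the floor of the category. If small meant anything below medium, all 12 labels in the text would fit, and the SAP never uses a category below small. That stands as a limit on the first point, which rests on reading the printed value as a lower limit. However, the documents define no such open-ended category, and it would leave the printed small value without a function. The statement that both 10-week means are below 2.59 is true on either reading.

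The SPT-R gap is also trivial, since 2.556 and 2.59 both round to 2.6. That is conceded; SPT-B is the clear case.

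On percent change, the sentence follows the explanation of negative values and could be taken to mean that none was negative, which is true of all 24 values. But it says positive, and zero is not positive. It is also fair to add that a 25th percentile of 0% puts roughly three quarters of the values at or above the highest baseline score, which is a demanding comparator.

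The Table 4 citation is probably a leftover of earlier numbering, because the same paragraph correctly assigns generalization effect sizes to Table 2. It is a slip that favours neither side. Finally, the tables print every value, and the SAP reports no significant generalization differences and low power, so a careful reader can recover the facts.

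**Conclusion.** The concern holds. The percent-change sentence is wrong as written for untreated items: 8 of 24 values called positive are 0%, including both 10-week medians and all six 25th percentiles in Table 4. It is true of treated items, where 12 of 12 are positive. The effect-size sentence is wrong for 2 of 6 means if the printed small benchmark is a lower limit, marginally for SPT-R and clearly for SPT-B. Its table reference is wrong on any reading.

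The consequence is descriptive only. These are text-to-table inconsistencies, not calculation errors. No comparison of SPT-R with SPT-B changes, no treated-item result changes, and the 10-week untreated mean effect sizes remain above zero. The correction is still worth making, because the two sentences govern what the report says about generalization at 10 weeks.

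**What to change.** **Effect Sizes section.** State that the untreated means reached the small benchmark at end of treatment and at 2 weeks in both conditions, and that both 10-week means were below it (SPT-R marginally, 2.556 against 2.59; SPT-B 2.107). Cite Table 2 in place of Table 4.

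**Percent Change Over Highest Baseline Performance section.** Limit the all-positive statement to Table 3. Add that for untreated items the 25th percentile was 0% at every time point, and that the median gain over highest baseline at 10 weeks was 0% in both conditions.

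Draw no further conclusion about maintenance of generalization; the intervals above do not support one.

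The cost is the wording of two sentences and one table reference, with no reanalysis.
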